3.2 Secondary Endpoints

3.2.1 At study entry, basic demographics and baseline laboratory values will be summarized using descriptive statistics (i.e., means, medians, and variability measures for continuous variable; rates and proportions for binary variables). Screening assessments to be completed within 21 days prior to study enrollment.

3.2.2 Overall survival will be assessed at 12 weeks, one year, and two years from the start of treatment.

3.2.3 Event-free survival will be defined as the rate of refractory disease, relapse (same definition of active disease as in the inclusion criteria in section 4.1), non-Hodgkin lymphoma development or death and will be assessed at 12 weeks, one year, and two years from the start of treatment.

3.2.4 Clinical response rate at end of treatment and 12 weeks from treatment initiation (clinical response defined as resolution of presenting signs/symptoms that defined

the Multicentric Castleman disease (MCD) attack) without relapse at 12 weeks. MCD attack/flare is defined in Section 4.1.1.

3.2.5 Radiologic response rate is the percentage of patients without relapse at end of treatment and 12 weeks from treatment initiation. Chest radiography and abdominal sonography will be used for staging. Per Revised response criteria for gross lymphadenopathy, response will be evaluated via complete survey of lymph nodes with measurements and physical assessment of other palpable masses with measurements.

Response criteria for lymph node response will be as follows: Complete response (CR)- disappearance of all evident disease; Partial response (PR)-at least 50% decrease in target lesions with no increase in non-target lesions, Stable disease (SD)- Neither sufficient shrinkage to qualify for PR nor sufficient increase to qualify for progressive disease (PD); PD- appearance of a new lesion or at least a 50% increase in lesion size.

3.2.6 Additional safety assessment will be graded by CTCAE v 5.0 through 12 weeks from the start of therapy.

3.2.7 Kaposi sarcoma exacerbation will be defined as new symptoms attributed to KS or clinically evident exacerbation of dermatologic or visceral disease. All disease flares will be biopsy confirmed whenever possible.

3.2.8 Quality of life will be assessed by the MCD symptom score, a patient-reported outcomes questionnaire, and PROMIS Global 10, at baseline (week 1), 15 days (week 3), end of treatment (week 5), 12 weeks, 6 months, and 24 months after treatment, and at the time of any relapse.

3.2.9 Hemoglobin (grams per deciliter (g/dL)), platelet count (microliters (μ l)), and C-reactive protein (CRP; milligrams per milliliter (mg/mL)) will be measured at baseline, day 15, and end-of-treatment.

3.2.10 Change in Kaposi sarcoma herpesvirus viral load will be measured in copies per milliliter at baseline, day 15, and end of treatment.

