7.1.7 Radiologic Disease Assessment (Revised response criteria for gross lymphadenopathy)

All patients will undergo baseline on-study chest radiography and abdominal sonography for staging. Response will be evaluated via complete survey of lymph nodes with measurements and physical assessment of other palpable masses with measurements (using a flexible metric ruler in two dimensions). Chest radiography and abdominal sonography will be repeated at completion of treatment.

Measurable disease will be defined as the presence of at least one measurable pathologic lymph node or other mass that can be accurately measured by physical exam in at least one dimension with the longest diameter a minimum size of 10mm caliper measurement by clinical exam (lesions which cannot be accurately measured with calipers should be recorded as non-measurable). All measurements should be recorded in metric notation using calipers. All baseline evaluations should be performed as close as possible to the treatment start and never more than four weeks before the beginning of treatment. The same method of assessment and the same technique should be used to characterize each identified and reported lesion at baseline and during follow-up. Clinical lesions will only be considered measurable when they are superficial and ≥ 10 mm diameter as assessed using calipers.

All measurable lesions by physical exam or maximum of five lesions should be identified as target lesions and will be recorded and measured in two dimensions at baseline. Target lesions should be selected on the basis of their size (lesions with the longest diameters) and should also be those that lend themselves to reproducible

repeated measurements. A sum of the product of diameters (SPD, as in the International Harmonization Product criteria) for all target lesions will be calculated and reported as the baseline SPD. The baseline SPD will be used as reference to further characterize the objective tumor response of the measurable dimension of the disease.

All other lesions (or sites of disease), including lesions evident only by chest x-ray or ultrasound given difficulties with reproducibility of radiographic studies in our setting, should be identified as non-target lesions and should also be recorded at baseline. Measurements are not required, and these lesions should be followed as 'present' or 'absent', or in rare cases 'unequivocal progression.'

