A similar strategy for response assessment based on target lesions documented by physical exam alone is currently being utilized at UNC Project Malawi for a clinical trial for lymphoma.

Response criteria for lymph node response will be as follows.

- Complete response (CR): Disappearance of all evident disease. Any pathological lymph node (LN), whether target or non-target, must have decreased to <10mm in diameter. Any non-target lesion evident by chest x-ray or ultrasound must also be documented to have resolved by repeat evaluation.
- Partial response (PR): At least a 50% decrease in SPD of up to six target lesions without any increase in size of non-target lesions.
- Stable disease (SD): Neither sufficient shrinkage to qualify for PR nor sufficient increase to qualify for PD.
- Progressive disease (PD): Appearance of a new lesion(s) >15mm in diameter, at least a 50% increase in SPD of more than one node, OR at least a 50% increase in diameter of a previously identified node >1cm. Given numerous causes of adenopathy in Malawi (particularly among HIV-infected individuals) and in order to exclude alternative non-lymphoma diagnoses, a concerted attempt to re-biopsy at the time of relapse or progression will be made unless patients refuse or the site is not amenable using locally available resources.

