10.5 Secondary Objectives

10.5.1 To better characterize MCD presentation in Malawi.

Basic demographics and baseline laboratory values will be summarized using descriptive statistics (i.e., means, medians, and variability measures for continuous variable; rates and proportions for binary variables).

10.5.2 To describe the efficacy of the risk-adjusted approach as determined by clinical and radiologic response rates, 90-day, one-year, and two-year EFS and OS.

An event for EFS is either relapse (defined as “MCD attack” in the Inclusion Criteria (section 4.1)), refractory disease, lost-to-follow-up (LTFU), or death. We will consider patients LTFU if they cannot be contacted by phone for three months. Given the high mortality associated with MCD and previously published literature supporting a strong association between LTFU and mortality in SSA, we will consider LTFU as a failure event for both EFS and OS.⁴³ Relapse for purposes of this study will be defined as recurrence of an “MCD attack” (Inclusion Criteria; section 4.1) requiring re-initiation of treatment, with a strong preference for biopsy-proven recurrence whenever possible. We will conduct survival analysis using Kaplan-Meier methods. Radiologic response will be assessed in parallel with clinical response with response criteria defined in section 7.1.7. We will assess the prognostic value of radiologic response for EFS and OS in Cox proportional hazards model.^{10,15,16}

10.5.3 To describe the safety, as determined by the rate of all AEs during a risk-adjusted approach to treatment of MCD in Malawi.

All AEs will be described up to 30 days after final dose of MCD-directed treatment.

10.5.4 To describe the rate of KS exacerbation, as defined by symptomatic or clinical (dermatologic or visceral organ) exacerbation of disease.

The rate of KS exacerbation will be reported as the number of KS cases requiring KS-specific treatment divided by the number of patients with pre-existing KS (as defined by personal history of KS, baseline presence of KS, or KS in lymph node biopsy). This will be estimated along with a 95% confidence interval for the proportion.

10.5.5 To describe the quality of life of patients with MCD before, during and after treatment with a rituximab-based, risk-adjusted treatment approach, as assessed by the MCD symptom score⁴² and PROPr instrument.⁴⁴

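### Section 3.2.5 defines radiologic response as freedom from relapse, which conflicts with the CR/PR/SD/PD criteria the analysis is to use, and no section states the numerator

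*Combined protocol and SAP*

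**What the plan says.** Section 3.2.5 of the protocol opens with the only sentence that defines the rate: "Radiologic response rate is the percentage of patients without relapse at end of treatment and 12 weeks from treatment initiation". It then says that response is evaluated by a nodal survey with measurements, and gives short definitions of CR, PR, SD and PD. PD there is "appearance of a new lesion or at least a 50% increase in lesion size".

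Section 7.1.7 gives the detailed version of the same four categories. PR is "At least a 50% decrease in SPD of up to six target lesions without any increase in size of non-target lesions". The first route to PD is "Appearance of a new lesion(s) >15mm in diameter"; the others are growth criteria based on SPD or on the diameter of a known node.

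Section 10.5.2 says that radiologic response will be assessed alongside clinical response using the "response criteria defined in section 7.1.7". It also fixes the meaning of relapse: "Relapse for purposes of this study will be defined as recurrence of an “MCD attack” (Inclusion Criteria; section 4.1) requiring re-initiation of treatment". Sections 3.2.3 and 10.5.2 both list refractory disease as an event distinct from relapse.

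Objective 2.2.5 is to describe radiologic response rates at end of treatment and at 12 weeks. Section 8.4 restricts efficacy evaluability to patients with measurable disease who received at least one dose and were re-evaluated.

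**The concern.** A response rate should count patients whose disease shrank by a stated amount. The opening sentence of 3.2.5 instead counts patients who did not have a particular clinical event. That event is defined by fever, nodal or organ enlargement and a further sign or symptom (Section 4.1.7), together with a need to restart treatment. None of this refers to change in node size from baseline.

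Two analysts could therefore report different radiologic response rates from the same data, one following 3.2.5 and the other following 10.5.2 and 7.1.7, and each could cite the protocol. A reader of the published rate would take it as CR plus PR, whereas the literal rule also admits patients with no nodal shrinkage.

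**Working it through.** The documents give no expected rate, target or power for radiologic response, so there is no planned figure to reproduce. The check is a comparison of the texts, followed by simple counting.

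**How each kind of patient is scored**

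| Patient | 3.2.5, opening sentence | CR or PR per 7.1.7 |
|---|---|---|
| CR or PR, no clinical relapse | response | response |
| CR or PR, clinical relapse | not response | response |
| SD, no clinical relapse | response | not response |
| Nodal PD, no clinical flare | response | not response |
| SD or PD, clinical relapse | not response | not response |

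Three rows disagree, two in one direction and one in the other. A refractory patient who has had no recurrent attack falls in the third or fourth row, because the protocol lists refractory disease apart from relapse.

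**Size of the difference.** For a common denominator N:

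literal rate − (CR+PR)/N = [SD without relapse + PD without relapse − CR/PR with relapse] / N

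Neither N nor any of these counts is in the documents. Section 10.2 gives 24 as the sample size for the safety test and 27 as planned enrolment; both serve here only as assumed denominators.

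- One non-relapsed SD patient: 1/24 = 4.2 points; 1/27 = 3.7 points.
- Assume N = 24, 14 with CR or PR (14/24 = 58.3%), none of these relapsing, and every patient outside CR, PR and SD relapsing. With 0, 2, 5 or 7 non-relapsed SD patients the literal rate is 14/24 = 58.3%, 16/24 = 66.7%, 19/24 = 79.2% or 21/24 = 87.5%. The gap is 0, 8.3, 20.8 or 29.2 points.
- The gap can reverse. Assume N = 24, 14 with CR or PR of whom 3 relapse clinically, 2 with SD and no relapse, and 8 with PD and relapse. The literal rate is (14 − 3 + 2)/24 = 13/24 = 54.2%, against 14/24 = 58.3%.

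**Progression.** A new 12 mm node is PD under 3.2.5, where any new lesion suffices. It does not meet the new-lesion criterion of 7.1.7, which needs more than 15 mm.

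**The neighbouring endpoint.** Clinical response (3.2.4) requires both resolution of the presenting signs or symptoms and no relapse at 12 weeks. The opening sentence of 3.2.5 has only a no-relapse condition.

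**The case against.** The strongest reply is that 3.2.5, read as a whole, intends a nodal assessment. It goes straight on to the survey of lymph nodes and the four categories, and 10.5.2 points to 7.1.7. On that reading the opening sentence is a drafting slip and any analyst would report CR plus PR. The probable intent may well be that. But it requires setting aside the only sentence that defines the rate, no section says which text governs, and the protocol nowhere states that response means CR or PR. The conflict and the missing numerator remain.

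Four stronger readings are tempting, and the documents do not support them.

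- A reader might infer that the literal rate is always at least as high as CR plus PR. It is not: a patient with nodal PR can still have a clinical attack, as the reversed example shows.
- A reader might infer that the flawed definition enters the planned Cox model of radiologic response for EFS and OS. If it did, relapse would sit in both predictor and outcome for EFS. But the sentence just before the model in 10.5.2 ties radiologic response to 7.1.7, so the text does not show this.
- A reader might want to quote a specific inflation. Any split of patients into categories is invented.
- A reader might say that only the 3.2.5 version fails to be radiologic. Under 7.1.7 the target lesions are measured by physical examination, and lesions seen only on X-ray or ultrasound are non-target, so this does not separate the two versions.

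**Conclusion.** The point holds as a conflict between an endpoint definition and the criteria the analysis is to use, together with an unstated numerator and two wordings of progression. Followed literally, 3.2.5 counts SD, and nodal PD without a flare, as radiologic response.

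The expected direction is upward, on the assumption that such patients outnumber CR/PR patients who relapse clinically. This is likely but not certain. The size is unknown: about 4.2 points per non-relapsed SD patient if N = 24, or 3.7 if N = 27, and 0 to 29 points over the assumed range of 0 to 7 such patients in 24.

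The endpoint is secondary and descriptive, with no test or power attached. The primary safety test, its sample size and the stopping boundaries are unaffected. The wording should be corrected because it is cheap to do and the reported rate is otherwise ambiguous.

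**What to change.** Replace the opening sentence of 3.2.5 with wording such as:

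> The radiologic response rate is the proportion with CR or PR per Section 7.1.7, at end of treatment and at 12 weeks, among patients with measurable disease who received at least one dose. SD and PD are non-response.

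Then make these consequential edits:

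1. **Denominator.** The sentence above includes treated patients who were never re-evaluated, whereas 8.4 excludes them. Either amend 8.4 so that they count as non-responders, or report the rate on both denominators. Adding a non-response rule to 3.2.5 alone would create a new conflict.
2. **One set of categories.** Replace the short CR/PR/SD/PD text in 3.2.5 with a reference to 7.1.7, so that a single PD definition applies to this endpoint. This concerns how the endpoint is scored, not when treatment stops.
3. **Target lesions.** Section 7.1.7 caps target lesions at five when they are selected but refers to up to six in the PR definition. These must be reconciled.
4. **The 12-week assessment.** The Time and Events Table schedules nodal measurement at 12 weeks, but not chest X-ray or ultrasound. CR in 7.1.7 needs imaging-evident lesions to be shown resolved on repeat evaluation. State that the 12-week assessment is by nodal examination, and how such lesions are then handled.
5. **Freedom from relapse.** Report it separately under its own name.

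The cost is a protocol amendment with its ethics review. No visit or measurement is added. The reported rate will probably be lower than under the literal wording.

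### Sections 3.2.5 and 7.1.7 give different rules for nodal progression, so the same measurements can be PD under one and not under the other

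*Combined protocol and SAP*

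**What the plan says.** Radiologic response at end of treatment and at 12 weeks is a secondary objective (section 2.2.5).

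Section 3.2.5 defines the endpoint. It first makes the radiologic response rate the percentage of patients free of relapse at those two times, then lists CR, PR, SD and PD. PR is "at least 50% decrease in target lesions with no increase in non-target lesions". PD is "PD- appearance of a new lesion or at least a 50% increase in lesion size".

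Section 7.1.7 introduces its own list with the same sentence, but the content differs. PR is "At least a 50% decrease in SPD of up to six target lesions without any increase in size of non-target lesions". PD is "Appearance of a new lesion(s) >15mm in diameter, at least a 50% increase in SPD of more than one node". A further route to PD applies to a single known node above 1 cm whose diameter grows by half or more. On the choice of targets, the same section says "maximum of five lesions should be identified as target lesions", measures them in two dimensions, and makes the baseline SPD the reference for response.

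Section 10.5.2 takes the radiologic response criteria from 7.1.7 and plans Cox models of EFS and OS on radiologic response. Section 8.4.1 also refers to 7.1.7. Section 5.7 lists disease progression as a reason to end treatment, without saying which definition applies.

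**The concern.** Two sections state a rule for the same response categories, and the rules do not agree. If the conflict is still there when the data are read, the choice between them can be made after the results are known.

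Two analyses are exposed: the description of radiologic response, and the Cox models in which response is the prognostic factor. If the response rate is built from the categories and all 27 planned patients are evaluable, one reclassified patient moves it by 1/27 = 3.7 percentage points.

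The word progression also appears in section 5.7. Nodes are measured on day 15, during treatment, so the definition can matter before treatment is complete.

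**Working it through.** The plan gives no figure to reproduce here. The check sets the rules side by side and then classifies a few hypothetical measurements. These are assumptions for illustration, not trial data.

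| Element | Section 3.2.5 | Section 7.1.7 |
|---|---|---|
| PD, new lesion | any | only above 15 mm |
| PD, growth | 50% in size, metric not given | 50% in SPD of more than one node, or 50% in diameter of one node above 1 cm |
| PR | 50% decrease, metric not given | 50% decrease in SPD |
| Number of targets | not given | five at selection, up to six in the PR rule |

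SPD is the sum over nodes of the product of the two diameters.

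**Case 1: a new small node.** Two targets shrink from 20 × 20 to 14 × 14 mm, and a new 12 mm node appears.
- SPD goes from 2 × 400 = 800 to 2 × 196 = 392 mm². The change is 392/800 − 1 = −51.0%.
- Section 3.2.5: PD, because any new lesion counts.
- Section 7.1.7: not PD, because 12 mm is not above 15 mm. It is PR if the new node is not counted as an increase in non-target lesions, and SD if it is.
- This result does not depend on how 3.2.5 measures size.

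**Case 2: growth in one node.** A single node goes from 20 × 20 to 25 × 25 mm.
- Area: 625/400 − 1 = +56.2%. Diameter: 25/20 − 1 = +25.0%.
- Section 3.2.5: PD if size means area, not PD if size means diameter.
- Section 7.1.7: not PD. Only one node has grown, and its diameter has risen by less than 50%.

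**Case 3: five or six targets, inside 7.1.7 only.** Five nodes of 30, 25, 25, 20 and 20 mm (equal diameters) each shrink by 30% in both dimensions. A sixth, of 18 mm, is unchanged.
- Five nodes: 900 + 625 + 625 + 400 + 400 = 2950 mm², falling to 0.49 × 2950 = 1445.5 mm², a change of −51.0%.
- Six nodes: 2950 + 324 = 3274 mm², falling to 1445.5 + 324 = 1769.5 mm², a change of −46.0%.
- The count can decide PR, but only if a sixth node is treated as a target. If the cap of five is followed at baseline, the wording in the PR rule is already met.

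**The case against.** The strongest reply is that the plan already says which rule governs. Sections 10.5.2 and 8.4.1 both name 7.1.7. Section 3.2.5 itself invokes the revised criteria for gross lymphadenopathy, which is the subtitle of 7.1.7. Its CR line also omits conditions found there (nodes below 10 mm, imaging lesions shown to have resolved), so the whole list can be read as a summary. Most of this stands, and an analyst following 10.5.2 would use 7.1.7. It does not remove the conflict. A summary that drops the 15 mm limit states a different rule, and it does so in the section that defines the endpoint.

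The reply is also right against several stronger readings that a reader might infer:

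- **That the PR thresholds conflict.** Both sections use 50%. If 3.2.5 meant diameter, the rules would diverge, since a 50% fall in SPD is a fall of only 1 − √0.5 = 29.3% in diameter when both dimensions shrink equally. But neither section states a diameter threshold for PR, and target lesions are defined only in 7.1.7, with SPD as the reference. The fault is a missing metric.
- **That five versus six is a difference between the two sections.** Section 3.2.5 gives no number. The inconsistency lies wholly inside 7.1.7 and is minor.
- **That small new nodes will be common.** Section 7.1.7 mentions the many causes of adenopathy in Malawi to justify re-biopsy at relapse or progression. It gives no rate. Such nodes can occur, and no more can be said.

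**Conclusion.** The PD rules in 3.2.5 and 7.1.7 contradict each other. The new-lesion conflict holds on any reading; the growth conflict in case 2 depends on reading size as area. Section 3.2.5 also leaves the PR metric unstated.

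The number of patients affected cannot be estimated, because the documents give no frequency of new nodes of 15 mm or less and no distribution of nodal change. The consequence is limited by the references to 7.1.7 and by the role of the endpoint. It is secondary, EFS events do not include nodal PD as such, and the primary safety endpoint and sample size do not depend on it.

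A reader might infer that the stated radiologic response rate changes with the choice of rule. As written it does not. Section 3.2.5 defines that rate by freedom from relapse, and section 10.5.2 defines relapse as a recurrent MCD attack that requires treatment to be restarted. The CR/PR/SD/PD categories do not enter. This is a separate defect in the same paragraph: the endpoint lists categories that its own rate does not use. The 3.7 points per patient therefore applies only once the rate is based on the categories.

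This should be corrected before response data are analysed, but it does not threaten the main conclusions of the trial.

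**What to change.** For the radiologic response endpoint and the Cox analysis:

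1. In section 3.2.5, replace the CR/PR/SD/PD list with a reference to section 7.1.7, which section 10.5.2 already names.
2. Reword the opening of 3.2.5 so that the radiologic response rate is based on those categories and not on freedom from relapse, and state which categories count as response. Without this step, removing the list would leave a rate that still ignores the criteria.
3. In the PR rule of section 7.1.7, make the number of target lesions agree with the number selected at baseline.

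Separately, where disease progression ends treatment (section 5.7), the sections must be reconciled so that it is clear which definition is meant. No clinical rule is proposed here.

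The cost is a few sentences in an amendment. No new data, visits or patients are needed.
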